**Table 4: Estimand of the Primary Analysis** 

Estimand attribute	Primary definition		Rationale (as needed)
Population	Patients with Huntington's disease with choreic movements		
Endpoint	Change from baseline (Visit 0 and Visit 1) to end of maintenance dose (Visit 4 and Visit 5) in TMC score		
Inter-current events	Event	Strategy	Rationale (as needed)
	Receipt of assigned study treatment	Treatment policy	This strategy applied to align the estimand with the application of the ITT principle.
	Prohibited concomitant treatment during the treatment period	While on treatment	This strategy applied up to the time of the prohibited concomitant treatment.
	Discontinuation from study	Hypothetical policy	This strategy applied for randomized and treated patients using a MMRM approach under MAR assumptions.
Summary measure	Difference in adjusted LS means between active arms and placebo from baseline to end of maintenance visit.		

The primary analysis of the primary efficacy endpoint will be based on a mixed-effect linear model for repeated measures (MMRM) to compare each active treatment group to placebo. The model will include the following factors: treatment group, visit, and treatment-by-visit interaction as fixed effects, and baseline TMC score as covariate. An unstructured (US) variance-covariance matrix will be used to model the within-patient errors. If no reliable results under the US assumption can be obtained, the Toeplitz (TP) covariance structure, followed by the autoregressive (AR1) and Compound Symmetry (CS) covariance structure will be used. The Kenward-Roger method will be used to estimate the denominator degree of freedom.

The least square mean (LSM) estimate for each treatment group and difference in LSM estimates at end of maintenance dose between active treatments and placebo group with their confidence intervals will be provided.

To preserve the family-wise error rate at the 0.05 level when comparing the two doses of SOM3355 versus placebo, statistical testing will be carried out using the Holm procedure. The smallest p-value of the two comparisons will be first compared at the two-sided 0.025 level and if statistically significant, the other p-value will be compared at the two-sided 0.05 level.

Sensitivity analyses on the primary efficacy endpoint will be conducted as follows:

- Primary endpoint will be analyzed using the observed cases (no imputations) using an analysis of covariance (ANCOVA) model.

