## 4.7.1 Primary endpoint

The primary endpoint is the change in Total Maximal Chorea (TMC) score from baseline (defined for each patient as the average of values at the screening visit (Visit 0) and the inclusion visit (Visit 1)) to the end of maintenance therapy (defined for each patient as the average of values at the end of Week 9 (Visit 4) and the end of Week 10 (Visit 5)).

As a result, the different factors included in the MMRM model (below) will be defined as following:

- Baseline TMC: calculated as (TMC V0 + TMC V1)/2,
- TMC at each following Visits: V2 (week 3), V3 (week 6), V4 (week 9), V5 (week 10)),
- Change from baseline TMC: [(TMC V4 + TMC V5)/2 Baseline TMC]

If the value at V5 is missing and V4 is not missing, then the value at V4 will be used for the calculation. If the value at V4 is missing and V5 is not missing, then the value at V5 will be used for the calculation. If both V4 and V5 values are missing, change from baseline TMC will be treated as missing.

The estimand of the primary efficacy analysis is defined according to ICH-E9-R1. The estimand reflects a mixed strategy for the inter-current events as presented in the table below.

Estimand attribute	Primary definition	Rationale (as needed)
Population	Patients with Huntington's disease with choreic movements	

Statistical Analysis Plan	Version 1.0		Page 18 of 37
Sponsor	SOM Biotech	Protocol No	SOMCT03

Estimand attribute	Primary definition		Rationale (as needed)
Endpoint	Change from baseline (Visit 0 and Visit 1) to end of maintenance dose (Visit 4 and Visit 5) in TMC score		
	Event	Strategy	Rationale (as needed)
	Receipt of assigned study treatment	Treatment policy	This strategy applied to align the estimand with the application of the ITT principle.
Inter-current events	Prohibited concomitant neuroleptic treatment during the treatment period	While on treat- men	This strategy applied up to the time of the prohibited concomitant treatment.
	Discontinuation from study	Hypothetical policy	This strategy applied for randomized and treated patients using a MMRM approach under MAR assumptions.
Summary measure	Difference in the change of TMC score from baseline to end of maintenance visit adjusted LS means between active arms and placebo		

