The primary analysis of the primary efficacy endpoint will be based on a mixed-effect linear model for repeated measures (MMRM) to compare each active treatment group to placebo. The model will include the following factors: treatment group, visit, and treatment-by-visit interaction as fixed effects, and baseline TMC score as covariate. An unstructured (UN) variance-covariance matrix will be used to model the within-patient errors. If no reliable results under the UN assumption can be obtained, the Toeplitz (TP) covariance structure, followed by the autoregressive (AR1) and Compound Symmetry (CS) covariance structure will be used. The Kenward-Roger method will be used to estimate the denominator degree of freedom.

The SAS code for the primary analysis is as follows:

PROC MIXED data=dataset method=REML;

CLASS subject treatment visit;

MODEL changeTMC = treatment visit treatment\*visit baselineTMC / ddfm=KR;

REPEATED visit / subject = subject type = UN;

LSMESTIMATE treatment\*visit "TMC change 200 mg vs Placebo" 0 0 -1 0 0 1 0 0 0 / cl elsm;

LSMESTIMATE treatment\*visit "TMC change 300 mg vs Placebo" 0 0 -1 0 0 0 0 0 1/cl elsm:

RUN;

Statistical Analysis Plan	Version 1.0		Page 19 of 37
Sponsor	SOM Biotech	Protocol No	SOMCT03

The least squares mean (LSM) estimate for each treatment group and difference in LSM estimates at end of maintenance dose between active treatments and placebo group with their confidence intervals will be provided. For the lowest p-value 97.5% CI will be provided and for the highest p-value 95% CI will be provided.

To preserve the family-wise error rate at the 0.05 level when comparing the two doses of SOM3355 versus placebo, statistical testing will be carried out using the Holm procedure. The smallest p-value of the two comparisons will be first compared at the two-sided 0.025 level and if statistically significant, the other p-value will be compared at the two-sided 0.05 level.

Descriptive statistics will be presented for the TMC score and changes from baseline by treatment group and by visit (including V6), on imputed data (as described in 4.1.). In addition, time profiles of the mean TMC scores with standard error of the mean (SEM) will be presented.

Sensitivity analyses on the primary efficacy endpoint will be conducted as follows:

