## Sensitivity #4

The primary efficacy analysis will be repeated using data without imputation for the visits of discontinued patients for the mITT population.

Subgroup analysis as defined in section 3.6 will be performed for the primary endpoint across all predefined groups, with a particular focus on comparing patients taking neuroleptics as concomitant medication during the study versus patients not taking neuroleptics during the study. For this subgroup, descriptive statistics for the TMC score and changes

Statistical Analysis Plan	Version 1.0		Page 20 of 37
Sponsor	SOM Biotech	Protocol No	SOMCT03

from baseline by treatment group and by visit (including V6) will be presented, as well as time profiles of the mean TMC scores with standard error of the mean (SEM) will be provided.

For the subgroup analysis assessing patients with correct versus incorrect down titration phase between V5 and V6, only descriptive statistics for TMC score on visits will be repeated on the mITT to show the evolution of the TMC score between V5 and V6 after IMP interruption.

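### The estimand limits TMC to the period before a prohibited treatment, but no derivation or model step makes that cut, and neither available handling of V4/V5 scores gives the declared while-on-treatment strategy

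*SAP*

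**What the plan says.** **Estimand.** The SAP 4.7.1 table names the intercurrent event as "Prohibited concomitant neuroleptic treatment during the treatment period". Protocol Table 4 has the wider "Prohibited concomitant treatment during the treatment period". Both assign *while on treatment* and give the same explanation: "This strategy applied up to the time of the prohibited concomitant treatment".

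**Derivation.** In the same SAP section, the endpoint is the mean of V4 and V5 minus the mean of V0 and V1. The only conditions attached concern missing scores: "If the value at V5 is missing and V4 is not missing, then the value at V4 will be used for the calculation", the mirror-image rule for V4, and "If both V4 and V5 values are missing, change from baseline TMC will be treated as missing".

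**Model.** "The model will include the following factors: treatment group, visit, and treatment-by-visit interaction as fixed effects, and baseline TMC score as covariate". The code opens with "PROC MIXED data=dataset method=REML" and has no flag or record selection for medication.

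**Elsewhere.** SAP 4.1.2 deals with early discontinuation and partial dates. SAP 2.3 makes prohibited treatment a possible reason for exclusion from the PP population. Under Protocol 5.7, withdrawal after a significant deviation is at the investigator's discretion, so a patient can take a prohibited drug and still be scored at V4 and V5.

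**The concern.** The estimand table says what the primary result is meant to estimate. A programmer, however, builds the dataset from the derivation rules, and those ask only whether a score exists. A V4 or V5 score taken after a neuroleptic was started does exist, so it would be averaged in and counted as response to the randomised arm.

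The label causes a second difficulty. The endpoint is fixed at V4/V5. A *while on treatment* value for a patient with an event in week 7 would be that patient's TMC before the event, and the plan has no place for such a value. The reported difference would therefore not be the declared estimand. Two programmers could also produce different primary results from the same SAP. The futility analysis in SAP 4.12 uses the primary method and would inherit the ambiguity.

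**Working it through.** **1. Is the cut made anywhere?**

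| Place | What it acts on | Removes post-event TMC? |
|---|---|---|
| SAP 4.7.1 derivation | missing V4 and/or V5 | No |
| SAP 4.7.1 MMRM text and code | treatment, visit, interaction, baseline | No |
| SAP 4.1.2 | discontinuation; moves an end-of-study or unscheduled value into the first missing visit | No; it could add one |
| SAP 6.1 | derived variables | No |
| Sensitivity #1 | missing values | No |
| Sensitivity #2 | observed cases | No |
| Sensitivity #4 | "The primary efficacy analysis will be repeated using data without imputation for the visits of discontinued patients for the mITT population" | No; it concerns discontinued patients |
| Sensitivity #3 with SAP 2.3 | PP population | May drop the whole patient; does not cut at the event; mITT unchanged |

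**2. What each handling gives for one patient.** These records are invented for illustration.

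- *Placebo:* baseline 14, V2 14, V3 13, neuroleptic from Day 50, V4 10, V5 9. Literal derivation: (10 + 9)/2 − 14 = −4.5. Last value before the event: 13 − 14 = −1.0. With V4 and V5 set to missing, the patient has no end-of-maintenance value and the MMRM relies on V2, V3 and the MAR assumption.
- *600 mg/day:* baseline 14.5, V4 12, event on Day 66, V5 9. Literal derivation: (12 + 9)/2 − 14.5 = −4.0. With V5 set to missing, the existing rule uses V4 alone: 12 − 14.5 = −2.5.

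The placebo record shows three different targets: treatment policy (−4.5), while on treatment (−1.0) and hypothetical (a model prediction). The plan names the second and has rules only for the first.

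**3. The plan's own figure.** SAP 1.4: difference 2.5, SD 3.5, two-sided α 0.025, t-test. With 39 per arm, the noncentrality is 2.5/(3.5·√(2/39)) = 3.15 on 76 df, and power is 80.5%. With 38 per arm it is 79.4%. The stated 39 is reproduced and is not in question.

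**4. Illustrative size.** Let p_P and p_A be the proportions starting a prohibited drug on placebo and on one active arm, and g the added TMC improvement. None of these is in the documents. I take g = 1.5 to 3.5; the 2.5 and 3.5 are the VMAT2-inhibitor effects quoted in SAP 1.4, not neuroleptic effects.

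- *All values used:* difference = 2.5 − g(p_P − p_A). The variance in each arm is 3.5² + g²p(1 − p), averaged over the two arms; 39 per arm.
- *After the cut (simplified):* users drop out of the t-test, so n = 39(1 − p) per arm, difference 2.5, SD 3.5.

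Example at 10%/3% and g = 3.5: difference = 2.5 − 3.5 × 0.07 = 2.255; SD = √[(13.35 + 12.61)/2] = 3.60; power 68.3%. After the cut, n = 35.1 and 37.8, and power is 77.4%.

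| Use, placebo/active | Difference, all values (g 1.5 to 3.5) | Power, all values (g 1.5 / 2.5 / 3.5) | Power after cut |
|---|---|---|---|
| 3%/0% | 2.46 to 2.40 | 78.8 / 77.5 / 76.1% | 79.8% |
| 5%/2% | 2.46 to 2.40 | 78.7 / 77.1 / 75.2% | 78.9% |
| 10%/3% | 2.40 to 2.26 | 76.2 / 72.6 / 68.3% | 77.4% |
| 15%/5% | 2.35 to 2.15 | 74.3 / 68.8 / 62.4% | 75.5% |
| 5%/5% | 2.50 | about 80 / 79.5 / 78.5% | 78.2% |
| 0%/5% | 2.58 to 2.68 | 82.8 / 84.0 / 85.1% | 79.4% |

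The fair comparison is with the last column, because the cut also loses data. At g = 1.5, in the four rows with more placebo use, the cut gains between about 0.2 and 1.3 points of power. In the last row the higher power comes from an inflated difference and is not a benefit.

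**The case against.** The SAP never says that post-event scores are kept. The estimand row stands in the same section as the derivation and could be read as the cut-off itself, and the dataset name in the code is a placeholder. That is fair: use of the scores is what the rules give when followed literally, not a declared intention. It does not remove the problem. No rule carries out the cut, and an implied cut followed by the MMRM would still be hypothetical, not while on treatment.

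The plan also has partial safeguards. Sensitivity #3 repeats the analysis in the PP population, the blinded data review assesses the impact of deviations, and neuroleptic users versus non-users is a planned subgroup (SAP 3.6). These help interpretation. However, PP exclusion is only potential and removes whole patients, the user subgroup mixes authorised with prohibited use, and none of them changes the mITT primary result.

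The objection on size largely stands. The drugs are prohibited throughout, Protocol 2.1.2 calls the evidence for neuroleptics on chorea limited, the larger values of g belong to another drug class, and the illustration gives every user the full effect at both V4 and V5. A reader might infer from the lower rows that the primary comparison is materially underpowered, or that the flaw always works against the drug. The documents support neither: they give no rate of use and no neuroleptic effect, and the direction depends on which arm has more use.

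**Conclusion.** The mismatch is established from the text. The declared strategy stops at the event, the written rules do not, and the model can deliver only treatment policy or hypothetical for an endpoint fixed at V4/V5. It should be corrected before database lock because it concerns the definition of the primary result.

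Its numerical effect is unknown. Dilution is the likelier direction if the drug works and poorly controlled placebo patients are the ones given a neuroleptic, but that is an assumption. At 3 to 5% use on placebo, with 0 to 2% on active, the illustrative power is 75 to 79% with all values against 79 to 80% after the cut. Larger losses need both high rates and VMAT2-sized effects.

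The event definition adds to the gap. Under the SAP row, a non-neuroleptic prohibited drug, such as a VMAT2 inhibitor started on study, has no strategy at all, although the protocol row covers it. Stable neuroleptics approved by the Steering Committee (Protocol 5.3.2) are authorised and are not this event.

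**What to change.** 1. In SAP 4.7.1, before the V4/V5 average, set to missing any TMC value at V2 to V5 recorded after the first intake of a prohibited treatment covered by the estimand row. The existing rule then uses V4 alone when only V5 falls after the event.
2. State that SAP 4.1.2 may not carry a post-event end-of-study or unscheduled value into a missing visit. Otherwise the value just removed could return.
3. Relabel the strategy for this event *hypothetical* (MMRM under MAR) and list the change in SAP 2.2 as a deviation from Protocol Table 4.
4. Reconcile the event definition in the SAP and protocol rows.
5. Keep the analysis of all recorded values as a sensitivity analysis.
6. Confirm start dates of prohibited treatments at the blinded data review meeting. Partial dates matter here, because SAP 4.1.2 can move an unknown start day to the first of the month and so place it before a visit.

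Extending the cut to TMC response, percentage change and TMS is optional. The estimand covers only the primary analysis, and responder status would need its own rule for missing values.

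The cost is SAP wording, one SAP 2.2 entry and one programming step. No new data are needed, since medication start dates are already collected. The downside is that a few recorded scores are replaced by the MAR assumption already used for study discontinuation; item 5 shows how much that matters.

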#### 5.3.1. Prohibited treatments

VMAT2 inhibitors such as tetrabenazine, deutetrabenazine, or valbenazine are forbidden within  $\underline{3}$  months prior to randomization and at any time during the whole study.

Neuroleptics indicated to treat chorea such as haloperidol, pimozide, or tiapride, and all other neuroleptics used off label as dopamine D2 receptor blockers to treat chorea are forbidden within  $\underline{2}$  months prior to randomization and at any time during the whole study.

The following treatments are forbidden within 1 month prior to randomization and during the whole study:

- All monoamine oxidase (MAO) inhibitors.
- Levodopa and dopa-agonist drugs: apomorphin, ropinirole, pramipexole, rotigotine.
- Reserpine
- Glutamate antagonists: amantadine, memantine, riluzole.
- Anti-arrhythmic drugs inducing bradycardia: diltiazem, verapamil, amiodarone, digitalis, quinidine, sotalol, disopyramide.
- Any other beta blocker antihypertensive medication.
- Central antihypertensive treatments: clonidine, methyldopa, rilmenidine.

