## 1.4 Planned sample size

Power calculation is based on results from previous trials that tested VMAT2 inhibitors (TBZ and deuterbenazine) on chorea in HD patients with TMC score as primary endpoint, which showed a standard deviation of 3.5 and 3.9 respectively, and a treatment effect compared to placebo in TMC score of -3.5 and -2.5 respectively.

The sample size will be a total of 129 patients. Eligible patients will be randomized in blinded fashion in a 1:1:1 ratio i.e. 43 patients in each arm (SOM3355 400 mg/day, SOM3355 600 mg/day, or placebo). Assuming a treatment difference of -2.5 points in the change from baseline of TMC score compared to placebo and a standard deviation of 3.5 (to ensure a clinically relevant effect of at least -2 in the study), 39 patients per arm will provide at least 80% power that at least 1 dose of SOM3355 will be significantly superior to placebo at the 2-sided 0.025 significance level. This is based on the use of a two-sided t-test for the mean TMC score change. For the primary endpoint, the overall type I error will be controlled using a Holm procedure. To account for a 10% dropout rate, 43 patients per arm (i.e., a total of 129 patients) will be enrolled.

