## 2.2 Deviations from the trial protocol with regard to statistical analyses

The following deviations from the protocol were identified as being important for the statistical analysis:

For the key secondary efficacy endpoint (Change from baseline in the Clinical Global Impression (CGI-C)) multiplicity adjustment will be applied.

Original text in protocol: The type I error will be set at 0.05 (two-sided) and the coverage level of confidence intervals to 95% for all secondary efficacy analyses. No multiplicity adjustment will be applied for the statistical inferences of the secondary efficacy endpoints.

Statistical Analysis Plan	Version 1.0		Page 9 of 37
Sponsor	SOM Biotech	Protocol No	SOMCT03

The revised definition in SAP only for key secondary endpoint: To preserve the family-wise error rate at the 0.05 level when comparing the two doses of SOM3355 versus placebo and comparing a primary endpoint and key secondary endpoint, statistical testing will be carried out using the Holm procedure for CGI-C if the primary endpoint is significant for both doses. The smallest p-value of the two comparisons will be first compared at the two-sided 0.025 level and if statistically significant, the other p-value will be compared at the two-sided 0.05 level.

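### The SAP narrows the primary estimand's intercurrent event from any prohibited treatment to prohibited neuroleptics without declaring it, so VMAT2 inhibitors and glutamate antagonists have no stated strategy

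*SAP*

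**What the plan says.** Protocol Table 4 names the event as "Prohibited concomitant treatment during the treatment period" and gives it a while-on-treatment strategy, with data used until that treatment begins. The table in SAP 4.7.1 keeps the strategy but names the event as "Prohibited concomitant neuroleptic treatment during the treatment period". The rationale cell in the same SAP row is not narrowed: "This strategy applied up to the time of the prohibited concomitant treatment".

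Protocol 5.3.1 treats the prohibited drugs as separate groups. One is the VMAT2 class: "VMAT2 inhibitors such as tetrabenazine, deutetrabenazine, or valbenazine are forbidden" from three months before randomisation and throughout the study. Neuroleptics used for chorea are a second group. The glutamate antagonists amantadine, memantine and riluzole appear in a third list, and exclusion criterion 3 in Protocol 5.2 counts them as antichoreic.

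SAP 2.2 begins "The following deviations from the protocol were identified as being important for the statistical analysis" and then gives one item: "For the key secondary efficacy endpoint (Change from baseline in the Clinical Global Impression (CGI-C)) multiplicity adjustment will be applied". For tetrabenazine and deutetrabenazine, SAP 1.4 reports "a treatment effect compared to placebo in TMC score of -3.5 and -2.5 respectively"; Protocol 9.2 has the same figures.

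**The concern.** One inserted word changes which data belong to the primary estimand. Tetrabenazine, deutetrabenazine, valbenazine, amantadine, memantine and riluzole are prohibited but are not neuroleptics, so the SAP event as worded does not reach them.

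The endpoint is chorea, and SOM3355 is being developed as a VMAT2 inhibitor. If a patient starts another VMAT2 inhibitor before Visit 4 and stays in the study, the V4 and V5 scores mix the two drugs, or mix placebo with an active antichoreic drug. On placebo this would shrink the treatment difference; on an active arm it would be credited to SOM3355. SAP 4.12 uses the primary method for the futility analysis, so the same ambiguity carries over there.

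The row also contradicts itself. Two programmers could build different primary datasets from it, one following the event cell and one the rationale cell.

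**Working it through.** **Step 1. Does anything else in the SAP give the other prohibited drugs a strategy?**

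- SAP 4.1.2 (missing data) covers premature discontinuation and partial dates. It removes no TMC value after a prohibited drug. It also assigns the end-of-study value of a discontinued patient to the first missing visit, so a score taken after starting such a drug could be placed at V4.
- SAP 4.7.1 gives the rule for a missing V4 or V5, the MMRM and its code. None of these has a cut-off step.
- Sensitivity analyses 1, 2 and 4 concern missing data only.
- SAP 2.3 lists patients on prohibited treatments of any class for potential exclusion from the per-protocol population, which feeds Sensitivity 3 only.
- Protocol 5.7 allows, but does not require, withdrawal for a significant protocol deviation.

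The primary mITT analysis therefore has no rule for these drugs.

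**Step 2. Reproduce the planning figure.** Inputs from SAP 1.4: difference 2.5, SD 3.5, 39 per arm, two-sided alpha 0.025, t-test.

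- Standard error = 3.5 × √(2/39) = 0.793
- Noncentrality = 2.5 / 0.793 = 3.15; critical t on 76 df = 2.287
- Power = 80.5% (38 per arm gives 79.4%). The stated 39 per arm for at least 80% is reproduced.

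**Step 3. Illustrate the size.** Let k be the excess of placebo over active patients who are on a VMAT2 inhibitor at V4/V5, each with the full effect E. The documents give no value for k, so 2 and 4 are assumptions (5% and 10% of 39).

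Shift = (k/39) × E; remaining difference = 2.5 − shift.

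| E | k | Shift | Difference left | Pairwise power |
|---|---|---|---|---|
| – | 0 | 0 | 2.50 | 80.5% |
| 3.5 | 2 | 0.18 | 2.32 | 73.8% |
| 3.5 | 4 | 0.36 | 2.14 | 66.1% |
| 2.5 | 2 | 0.13 | 2.37 | 75.9% |
| 2.5 | 4 | 0.26 | 2.24 | 70.6% |

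An equal excess in an active arm shifts the estimate by the same amount in favour of SOM3355. No effect is given for amantadine, memantine or riluzole, so none is computed.

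**Step 4. The fair comparator.** Cutting these patients off also costs information. In a simple t-test with the difference kept at 2.5, 37 against 39 patients gives about 79% power (standard error 3.5 × √(1/37 + 1/39) = 0.803), and 35 against 39 gives about 78% (standard error 0.815). The power cost of the narrowed wording is therefore about 79% against 74%, or 78% against 66%.

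**The case against.** The strongest reply is that the consequence is inferred from silence. A reader might infer that the SAP has decided to count post-VMAT2 scores as response to the randomised arm. It does not say so: the rationale cell is still general, and the SAP states no removal step for neuroleptics either. This stands. What the text supports is an ambiguous row with no data-handling rule.

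Existing safeguards also count for something. Prohibited treatments of every class go to the blinded review, the per-protocol analysis may drop those patients, and concomitant medications are listed with start and stop dates. The problem would be visible and partly tested, but none of this supplies a rule for the primary analysis.

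The illustration is one-sided. It puts the whole excess on placebo, with the full effect. With 3 placebo and 1 active patient, the loss is 0.18 points, not 0.36; with equal numbers it is zero. It is also pairwise, whereas the plan's target is success for at least one dose. If both doses truly have the -2.5 effect, which is an assumption, simulated power for at least one dose is about 92%, falling to about 87% and 81% for 2 and 4 patients at -3.5. A reader might infer that the trial drops below its 80% target; on that measure it does not.

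SAP 2.2 covers deviations judged important and does not claim to list every one. But a change to the primary estimand is important by any ordinary standard.

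**Conclusion.** The point holds as a conflict between the SAP and the protocol on the primary estimand. The event is narrower in the SAP, the change is not declared, and the excluded classes have no strategy in the primary analysis. That rests on the text alone.

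The size is unknown. It depends on the between-arm excess of patients starting these drugs and on how much of the effect they show by V4/V5. If nobody starts one, or numbers balance, the treatment difference is not shifted. The 0.18 and 0.36 point figures are conditional illustrations, not forecasts.

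Two further inferences are not supported. A reader might conclude that the omitted drugs have the largest known TMC effect. The documents give TMC effects only for tetrabenazine and deutetrabenazine, so they cannot be ranked against neuroleptics or glutamate antagonists. A reader might also count a dose increase of an authorised neuroleptic as part of the narrowing. Protocol Table 4 does not name that event either, so the SAP has not removed it.

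**What to change.** Before unblinding, do one of the following in the SAP 4.7.1 table:

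1. Restore the Protocol Table 4 event, that is, any prohibited concomitant treatment. This also cuts TMC data at the start of prohibited drugs not listed as antichoreic, such as clonidine or digitalis.
2. Define the event as prohibited antichoreic treatment per Protocol 5.3.1 (VMAT2 inhibitors, neuroleptics, amantadine, memantine, riluzole), and declare and justify the change in SAP 2.2.

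In either case, make the event and rationale cells agree. State that TMC values after the start date of such a drug are set to missing in the primary MMRM dataset, including any end-of-study value that SAP 4.1.2 would otherwise move to a scheduled visit.

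The cost is one table row, one sentence on data handling and a drug-code list agreed at the blinded data review. Start dates are already collected, so no new data are needed. Fixing the list before unblinding also avoids a data-driven choice of event.

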## 4.7.2.3 The percentage of change in TMC score

The percentage of change in TMC score is defined as:

100 \* (TMC score at Visit x – TMC score at Baseline) / TMC score at Baseline. CONFIDENTIAL

Statistical Analysis Plan	Version 1.0		Page 22 of 37
Sponsor	SOM Biotech	Protocol No	SOMCT03

"Baseline" is the average score between V0 and V1, "Visits x" are V2, V3 and the average score between V4 and V5 or V4, V5 in case of missing visit.

For the analysis of the percentage of change in TMC score, descriptive statistics and the same MMRM model, as described for the primary endpoint will be used.

This analysis will be repeated on the PP population.

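### The primary MMRM fits one baseline TMC slope to all modelled visits, and its fallback covariances assume one variance: a cheap precision and robustness improvement, not a defect that invalidates the test

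*SAP*

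**What the plan says.** SAP 4.7.1 specifies an MMRM with "treatment group, visit, and treatment-by-visit interaction as fixed effects, and baseline TMC score as covariate". The SAS MODEL statement agrees: baseline TMC is a main effect only, with no baseline-by-visit term. Protocol 9.4.1 has the same model.

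The first-choice covariance is unstructured, so each visit has its own variance. If that gives no reliable result, "the Toeplitz (TP) covariance structure, followed by the autoregressive (AR1) and Compound Symmetry (CS) covariance structure will be used". As named, each of these has a single variance for all visits.

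The LSMESTIMATE rows have nine coefficients (3 arms × 3 visits) and the contrast falls on the third visit. SAP 4.7.2.3, which reuses the model, gives the levels as V2, V3 and "the average score between V4 and V5 or V4, V5 in case of missing visit". However, the list of model factors in 4.7.1 names V4 and V5 as separate visits. The code and 4.7.2.3 support three levels. The list does not.

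Sensitivity #1, #3 and #4 reuse the same MMRM. Sensitivity #2 is an ANCOVA on the endpoint alone. SAP 4.7.2.5 repeats the model for TMS, gait and dystonia, and SAP 4.12 uses the primary-endpoint code for futility.

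**The concern.** The three modelled levels are not alike. V2 is one rating at the end of up-titration, V3 is one rating, and the endpoint normally averages two. If the relation between change and baseline differs across them, a shared slope adjusts the endpoint partly from earlier visits. Part of any chance baseline imbalance then stays in the dose–placebo difference, which appears as lost precision.

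Under a fallback covariance, the endpoint would also take its standard error partly from V2 and V3. Averaging two ratings reduces rating error at the endpoint, while a growing spread of true change over time acts the other way. Equal variance would be a coincidence, and the sign of the error cannot be known in advance.

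At stake are the precision of the primary contrast and of every analysis that reuses the model and, only if the fallback is triggered, the error rate.

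**Working it through.** **The plan's own figure.** SAP 1.4 states "Assuming a treatment difference of -2.5 points in the change from baseline of TMC score compared to placebo", an SD of 3.5 and a two-sided level of 0.025. It adds: "This is based on the use of a two-sided t-test for the mean TMC score change". The normal approximation is 2 × (2.241 + 0.842)² × (3.5/2.5)² = 37.3, so 38 per arm. The exact t-test gives 79.4% power at 38 and 80.5% at 39, which reproduces "39 patients per arm will provide at least 80% power that at least 1 dose of SOM3355 will be significantly superior to placebo". Then 39 × 1.10 = 42.9, matching "1:1:1 ratio i.e. 43 patients in each arm". The planning standard error is 3.5 × √(2/39) = 0.793.

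**Slope constraint, formula.** With complete data and covariance Σ, the shared slope is a weighted mean of the visit slopes, with weights proportional to Σ⁻¹1. Let d be its distance from the true endpoint slope and σ_b the baseline SD. The excess variance of the dose–placebo difference is d² × 2σ_b²/n.

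**Slope constraint, simulation.** Assumptions not in the documents: baseline SD 3.5 or 4.5, residual correlation 0.6, V2/V3 residual SD 1.2 times that at the endpoint, and the slopes shown. Total endpoint SD is 3.5, with 39 per arm, complete data and 1,000 runs per row.

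| Slopes V2/V3/end | Baseline SD | SE, common slope | SE, by-visit slopes | Power, common | Power, by-visit |
|---|---|---|---|---|---|
| −0.2/−0.2/−0.2 | 3.5 | 0.777 | 0.777 | 82.1% | 82.0% |
| −0.2/−0.2/−0.2 | 4.5 | 0.766 | 0.767 | 83.8% | 83.2% |
| −0.1/−0.15/−0.3 | 3.5 | 0.758 | 0.757 | 83.9% | 84.4% |
| −0.1/−0.15/−0.3 | 4.5 | 0.735 | 0.732 | 86.7% | 87.0% |
| −0.1/−0.2/−0.5 | 3.5 | 0.696 | 0.687 | 90.3% | 91.5% |
| −0.1/−0.2/−0.5 | 4.5 | 0.624 | 0.608 | 95.7% | 96.3% |

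Mean bias is about zero, and type I error is 0.022 to 0.026 under both models.

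The formula reproduces the last row. The weights are 0.20/0.20/0.61, the shared slope is −0.362 and d = 0.138. Excess variance is 0.138² × 2 × 20.25/39 = 0.020, on 2 × 7.19/39 = 0.369. The SE ratio is √(0.389/0.369), about 1.026.

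A second set, with a stable trait, decaying correlation and rating error, gave variance ratios of 1.004 to 1.052 (SE up to √1.052 = 1.026) and at most 1.4 points of power (88.5% to 89.9%). A third gave 0.688 under both models when slopes were equal, and a gain of about 3 to 5% when they differed.

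The 5% is not a ceiling. Take the steepest slopes and set the V2/V3 residual SD to 0.8 times the endpoint's. The weights become 0.47/0.47/0.06 and d = 0.33. The SE ratio is then √(1 + 0.068/0.471) = 1.07 at baseline SD 3.5 and √(1 + 0.113/0.369) = 1.14 at 4.5. Even there the standard errors (0.734 and 0.694) stay below the planning value of 0.793.

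**Baseline-related dropout.** A deliberately adverse simulation used 43 per arm and baseline SD 4. Endpoint dropout depended only on baseline, in opposite directions in active and placebo. At 10% dropout the common slope gave a bias of 0.13 to 0.18 TMC points, against −0.04 to 0.01 with by-visit slopes. At 20% it gave 0.28 to 0.47, against −0.03 to 0.03.

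**Fallback variance, if used.** The SE ratio is approximately √(mean of the visit variances / endpoint variance).
- V2/V3 SD 1.2 times the endpoint's: √[(1.44 + 1.44 + 1)/3] = 1.137. The simulated SE is 0.844 against 0.744 (+13%), and power about 79% against 86%.
- V2/V3 SD 0.8 times: √[(0.64 + 0.64 + 1)/3] = 0.872. The simulated SE is 0.651 against 0.754 (−14%). By formula the critical value becomes 2.241 × 0.872 = 1.954, a true error of about 5% at nominal 2.5%. The simulation gave about 6%, with Monte Carlo error of about 1 point (250 runs).
- Equal SDs: 0.743 against 0.748, no material difference.

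The simulations covered Toeplitz and CS. AR(1) was not run.

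**The case against.** The strongest reply is that this is a precision preference. Randomisation removes average bias, type I error is held, and the trial was sized on an unadjusted t-test whose standard error of 0.793 exceeds every common-slope value above. With complete data that stands. It need not hold once baseline-related dropout differs by arm.

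Several stronger readings are tempting, but the documents do not support them:
- A reader might infer that regression to the mean must steepen the slope with time. It does so only if correlation with baseline decays over weeks 3 to 10, and no correlations are given. With a stable trait plus independent rating error, covariance with baseline is the same at every visit. Averaging V4 and V5 does not change it, so the slopes are equal.
- A reader might count residual error from chance imbalance as a second harm beside the variance inflation. The formula shows that they are the same quantity.
- A reader might take the rating-error variance at the endpoint to be exactly half. That needs independent errors one week apart, and SAP 4.7.1 uses V4 or V5 alone when the other is missing.
- A reader might apply the 13 to 14% figures to the planned analysis. Unstructured comes first, with six parameters for about 117 to 129 patients, so failure is unlikely. It is more plausible in small subgroups: six countries average 129/6 = 21.5 patients.

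Sensitivity #2 already has its own slope and residual variance. It is a useful check, but it does not carry the primary claim.

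**Conclusion.** Both structural points hold under the three-level reading. The shared slope also applies if V4 and V5 are modelled separately, but the contrast between an average and single ratings does not.

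The slope constraint costs nothing if slopes are equal. If they differ, it costs about 0 to 5% in standard error and 0 to 1.4 points of power across the simulated scenarios, and more only in an extreme pairing of steep slopes with less variable early visits. Bias of roughly 0.15 TMC points at 10% dropout appears only in the adverse pattern of opposite, baseline-related dropout.

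The variance constraint is potentially larger, about 13 to 14% in either direction, but depends on an unlikely failure of the unstructured fit. All slopes, correlations, SD ratios and dropout patterns are assumptions.

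A reader might conclude that the primary test is invalid. It is not, and the sample size is unaffected. The change is worth making because it is nearly free before unblinding and would look data-driven afterwards.

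**What to change.** Before unblinding:
- In SAP 4.7.1, add `baselineTMC*visit` to the MODEL statement and to the prose. Under three levels the LSMESTIMATE rows stay as they are.
- Carry the term, with the relevant baseline, into 4.7.2.3 and 4.7.2.5, and into the futility code of 4.12 if that analysis has not yet been run.
- Replace the fallback list with TOEPH, ARH(1) and CSH.
- State in 4.7.1 that the modelled visits are V2, V3 and the V4/V5 average, so that the factor list agrees with the code. If four levels are intended, the contrast rows must be rewritten and the new term uses three degrees of freedom.
- Record the departure from Protocol 9.4.1 in SAP 2.2.

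The cost is two degrees of freedom and SAP wording. No new data are needed.
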